- vADA samples will be collected at baseline visit and evaluation visits prior to infusion; any samples that are confirmed positive for ADA will also be tested for neutralizing antibodies. The test will be performed in the Takeda-designated central laboratory.
- \*Plasma lyso-Gb3 will be assessed in the Takeda-designated central laboratory.
- x An early morning spot urine sample will be obtained to measure protein and creatinine levels. Measurement of urine protein/creatinine ratio will be performed as part of urinalysis (see Appendix 2 for details on urinalysis).
- yTests for hepatitis B surface antigen with confirmation by hepatitis B viral DNA load, HCV antibody with confirmation by HCV ribonucleic acid polymerase chain reaction testing, and human immunodeficiency virus antibody will be performed in the local laboratory.

Sampling time points a Pre-infusion Durin		During infusion	End of Infusion	Post-infusion					
(from start of infusion)	0 min	20 mins	40 mins	50 mins	60 mins	90 mins	120 mins	240 mins	360 mins
Window		±1 min	$\pm 1 \min$	±2 mins	±2 mins	±2 mins	±2 mins	±2 mins	±3 mins
≥18 years old	•	•	•	•	•	•	•	•	•
<18 years old	•		•	•	• ~	A •	•	•	•

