Data collected in clinical trials to-date indicate that REPLAGAL remains safe and well-tolerated during long-term use. As with other intravenously (IV) administered protein therapeutics, the identified and potential risks of treatment with REPLAGAL include occurrence of infusion-related reactions (IRRs), cardiac ischemic events and arrhythmias triggered by IRRs, and potential development of neutralizing antibodies (NAbs) that may compromise efficacy. Of these, IRRs are idiosyncratic and allergic-type hypersensitivity reactions which may be defined as any new signs or symptoms experienced by subjects during the infusion or any new events occurring on the first day of administration of pharmacologic or biologic agents. Infusion-related reactions are the most commonly observed adverse drug reactions associated with REPLAGAL and generally occur within the first 2 to 4 months after initiation of treatment with REPLAGAL. The clinical experience has indicated that IRRs can be mitigated with a combination of infusion-rate control and medications such as antihistamines, antipyretics or low-dose corticosteroids. Cardiac ischemic events and arrhythmias triggered by IRRs have been also reported as risks associated with REPLAGAL treatment in patients with pre-existing cardiac manifestations of Fabry disease. The majority of these events were mild in severity, nonserious, and resolved. Cardiac events triggered by IRRs are possibly due to the hemodynamic stress caused by infusion. Additionally,

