The antibody status, including binding antibody (BAb) and neutralizing antibody (NAb) status, will be summarized as categorical variable by positive and negative at baseline, by transient positive and persistent positive during the study period, and by treatment-induced positive and treatment-boosted positive at each post baseline visits. The antibody titer will be summarized as continuous variable at baseline, and by any positive, by treatment-induced positive and treatment-boosted positive each post baseline visits. *Antibody data, including* BAbs and *NAbs, will also be presented in the form of individual subject listings.*

Antibody status (including binding antibody and neutralizing antibody status) will be defined as follows:

- treatment-induced positive: pretreatment is negative, post treatment become positive
- treatment-boosted positive: pretreatment is positive, post treatment Ab titer increases ≥ 4 folds compared to pretreatment
- persistent positive: at least positive two times (>16 weeks), including last time point tested, or positive at last timepoint tested

TAK675-3001	Page 22 of 27
Statistical Analysis Plan Amendment 1	1-Feb-2024

• transient positive: at least tested positive once, last time point tested is negative

Below are more details regarding the definitions provided above:

- Treatment-induced positive: baseline negative and at least one post-baseline positive
- Treatment-boosted positive: at least one post-treatment positive with Ab titer increases ≥ 4 folds compared to pre-treatment
- Persistent and transient positive: baseline not necessarily negative
- Persistent positive: the duration between first and last post-treatment positive > 16 weeks. The last post-treatment will be the last time point tested.
- Persistent positive: This also include only if the last time point tested positive, regardless of outcome of previous tests.
- Transient positive: at least one post-treatment positive, but last time point tested is negative
- Transient positive exclude the subjects that fulfilled the condition of persistent positive.

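### The ADA persistent/transient rule reduces to the result of the last sample, so its 16-week criterion never operates

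*SAP*

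**What the plan says.** SAP 6.6.3 summarises binding and neutralising antibody status over the study period as transient or persistent positive. The summary definition is "persistent positive: at least positive two times (>16 weeks), including last time point tested, or positive at last timepoint tested".

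The explanatory bullets below it repeat both alternatives:

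- Duration: "Persistent positive: the duration between first and last post-treatment positive > 16 weeks. The last post-treatment will be the last time point tested".
- Last sample: "Persistent positive: This also include only if the last time point tested positive, regardless of outcome of previous tests".

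The other class is defined as "Transient positive: at least one post-treatment positive, but last time point tested is negative", and a final bullet adds "Transient positive exclude the subjects that fulfilled the condition of persistent positive".

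On sampling, the Protocol (section 1.2, Table 1 footnotes) says "ADA samples will be collected at baseline visit and evaluation visits prior to infusion". Protocol 8.1.3.2 puts the evaluation visits at Weeks 8, 16, 28, 40 and 52, which gives five post-baseline samples per completing subject.

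**The concern.** The two routes to *persistent* are joined by *or*, but the first contains the second as one of its own conditions. A criterion built that way cannot change any classification, although the SAP states its 16-week threshold twice. What is left is the result of the final sample.

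The exclusion bullet points the same way. It removes persistent subjects from the transient class, but as written nobody can be in both, because one class needs a positive last sample and the other a negative one. The bullet has work to do only if a subject with a negative last sample can be persistent through duration. That suggests, without proving, that a free-standing duration criterion was intended.

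Antibody assessment, including neutralising status, is a listed secondary safety endpoint (Protocol 3.2, SAP 1.2.2). Protocol 2.2 names the "potential development of neutralizing antibodies (NAbs) that may compromise efficacy" among the risks of treatment. The transient/persistent split is the one summary in SAP 6.6.3 that is meant to describe how long a response lasts. A long response that has cleared by Week 52 would appear there as transient.

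**Working it through.** The documents give no figure to reproduce here, so the check is to apply the rule to every possible sequence of results.

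**Inputs.** Samples at Weeks 8, 16, 28, 40 and 52 (Protocol 8.1.3.2), taken at nominal weeks, with a result at each. Classification rules from SAP 6.6.3:

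- A (duration): at least two positives, last positive week − first positive week > 16, and last sample positive.
- B (last sample): last sample positive.
- Persistent = A or B. Transient = at least one positive and last sample negative.

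**Number of patterns.** 2^5 = 32, less the all-negative one, leaves 31.

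**Rule B.** Week 52 is positive and the other four samples are free: 2^4 = 16 patterns.

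**Rule A.** Week 52 is positive and the first positive comes more than 16 weeks earlier:

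| First positive | Span to Week 52 | Patterns |
|---|---|---|
| Week 8 | 44 weeks | 2^3 = 8 |
| Week 16 | 36 weeks | 2^2 = 4 |
| Week 28 | 24 weeks | 2^1 = 2 |
| Week 40 | 12 weeks | fails |
| Week 52 only | 0 weeks | fails |

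A is met in 8 + 4 + 2 = 14 patterns, all of them among the 16 of B. Patterns meeting A but not B: 0. So persistent = 16 and transient = 31 − 16 = 15. No pattern meets both class definitions, so the exclusion bullet excludes nobody.

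The two persistent patterns that fail A are Week 52 alone and Weeks 40 and 52 only (12 weeks).

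**Transient patterns with a span above 16 weeks.** Week 52 is negative:

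| First to last positive | Span | Patterns |
|---|---|---|
| Week 8 to Week 28 | 20 weeks | {8, 28}, {8, 16, 28} |
| Week 16 to Week 40 | 24 weeks | {16, 40}, {16, 28, 40} |
| Week 8 to Week 40 | 32 weeks | {8, 40}, {8, 16, 40}, {8, 28, 40}, {8, 16, 28, 40} |

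That is 2 + 2 + 4 = 8 of the 15. Visit windows do not alter this. The shortest span, Week 8 to Week 28, is 140 days; with ±4 days at each end it is at least 132 days, above 16 × 7 = 112. Week 8 to Week 40 ranges from 213 to 235 days (30.4 to 33.6 weeks).

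**Subjects who stop early.** The redundancy does not depend on reaching Week 52. If the last sample is at Week 40, A is met in 6 patterns, all within the 8 of B. If it is at Week 28, A is met in 2, all within the 4 of B.

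**With the last-sample condition removed from A.** The 8 patterns move, giving 16 + 8 = 24 persistent and 15 − 8 = 7 transient.

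**Size per subject.** One of 20 is 5 percentage points. Antibody summaries are split by age group (SAP 6.6), with the subgroup as denominator (SAP 9.2.1). If the group under 18 is at its planned minimum of 25% × 20 = 5, one subject there is 20 percentage points.

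**The case against.** The strongest reply is that the rule is redundant but workable. It gives one answer for every pattern, the last-sample condition is written out in both the summary and the bullets, and the Protocol defines neither term. On that view last-sample status is simply the sponsor's definition, and the exclusion bullet only restates that the classes are exclusive. The literal reading is indeed determinate, and intent cannot be proved from the text. But a definition that states a 16-week threshold twice and never applies it needs reconciling whichever meaning is wanted.

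Several limits on impact also stand:

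- The 31 patterns are not equally likely. The documents give no antibody incidence, and the number of affected subjects could be zero.
- Five of the 8 long-span patterns have a negative sample between positives. Only {8, 16, 28}, {16, 28, 40} and {8, 16, 28, 40} are uninterrupted, so not all 8 show continuous positivity.
- The rule errs in both directions, since a single positive at Week 52 counts as persistent.
- By-visit antibody status, treatment-induced and treatment-boosted status, titres and listings are all still produced. The table of infusion-related reactions uses positive/negative status, and no stated analysis takes the persistent/transient class further.
- Protocol 2.2 goes on to say that no loss of efficacy from neutralising antibodies is apparent so far.
- The SAP tests no hypothesis, and the primary endpoint, serious TEAEs, is unaffected.

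These points bound the consequence. They do not make the duration criterion operate.

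**Conclusion.** The concern holds. As written, *persistent* means last sample positive and *transient* means last sample negative after any positive. The 16-week criterion is decisive in 0 of 31 patterns, and 8 of the 15 transient patterns span 20 to 32 weeks. The containment follows from the wording alone. The counts assume the five scheduled samples with a result at each. How many real subjects are affected depends on how many turn negative late after a long run of positives, which the documents do not allow one to estimate. The effect is confined to a descriptive secondary safety table, so this should be corrected but does not threaten the trial's main conclusion.

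**What to change.** In SAP 6.6.3, remove from the duration criterion the qualifier requiring the last time point to be included, and delete the sentence "The last post-treatment will be the last time point tested". Then define:

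- **Persistent:** two or more post-baseline positives with the first and last more than 16 weeks apart, whatever the last result; or positive at the last time point tested.
- **Transient:** any other post-baseline positive.

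This makes both the stated threshold and the exclusion bullet operate. Footnote the subjects who are persistent only through a single positive at the final sample, since their duration is unknown. It would also help to mark in the listing those who qualify by span but have a negative sample in between.

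If last-sample status is what the sponsor wants, the alternative is to drop the 16-week text and rename the categories accordingly.

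The cost is SAP wording and one derivation, with no new samples. Under the revised definition the persistent count can only stay the same or rise.

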6.6.4 Extent of Exposure and Compliance

Treatment compliance and exposure summaries will be presented. For each subject, the subject's percent of compliance, reflecting the subject's willingness to accept the intravenous infusion at each infusion visit, will be calculated as follows for up to 52 weeks:

Compliance =

[(Number of Complete Infusions Received) / (Expected Number of Infusions)] ×100

Note: Expected number of infusions is defined as the number of infusions that the subject would have received up to the date of the subject's withdrawal or completion from the study. A non-complete / partial infusion is defined when the infusion has been withdrawn / stopped and not completed.

The number and percentage of subjects who received $\geq 80\%$ of scheduled infusions (not including partial infusions) will be reported. In addition, the total number of missed infusions will be categorized as 0, 1, 2 to 5, and >5 and summarized by n and the percentage in each category. The number of subjects with missed infusions will also be summarized.

The duration (in months) of drug exposure to REPLAGAL will be calculated as follows:

Exposure (months) = [(Date of the last dose – Date of first dose) + 1]/30.4375

The exposure data and the total number of infusions received will be summarized by descriptive statistics. The actual dose and per protocol dose amount (mg/kg) are defined as the weight adjusted **CONFIDENTIAL**

TAK675-3001	Page 23 of 27
Statistical Analysis Plan Amendment 1	1-Feb-2024

actual dose. For actual dose amount, the dose of REPLAGAL will be based on the last available weight on or prior to each infusion date. For protocol dose amount, the first dose of REPLAGAL will be based on the subject's weight at screening. The actual and per protocol dose amounts (mg/kg) and durations of infusion (minutes) will be averaged across the non-missing infusions for each subject and then summarized by the descriptive statistics across all subjects. All exposure data will be presented in a by-subject listing.

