### 7. DISCONTINUATION OF STUDY INTERVENTION AND SUBJECT DISCONTINUATION/WITHDRAWAL

## 7.1 Discontinuation of Investigational Product

If investigational product is discontinued, regardless of the reason, the evaluations listed for Week 52 (Table 1) will be performed as completely as possible. Whenever possible, all discontinued subjects should also undergo the protocol-specified safety follow-up 14 days (+7 days) after the last dose/infusion. Comments (spontaneous or elicited) or complaints made by the subject must be recorded in the source documents. The reason for discontinuation, date of discontinuation of the investigational product, and the total amount of investigational product administered must be recorded in the source documents.

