## 8.1.3 Treatment Period

# 8.1.3.1 REPLAGAL Infusion EOW (±4 days) from Week 0 Through Week 52

The treatment period will be up to 52 weeks during which subjects will receive EOW ( $\pm$ 4 days) IV infusions of REPLAGAL at the clinical site. The first dose of REPLAGAL will be based on the subject's weight at baseline. A change in subject weight of  $\geq$ 5% from baseline or the last weight used to recalculate the dose will require a recalculation of the dose by the clinical site.

# 8.1.3.2 Evaluation Visits at Week 8, 16, 28, 40, and 52

At evaluation visits, all study procedures, assessments (except for post-infusion vital signs), and sample collection (except for post-infusion PK sample collection on Week 28) outlined in Table 1 should be completed prior to administering an infusion, except on Week 40 and 52 visits where REPLAGAL infusion should maintain the  $\pm$ 4 days window period while the evaluation procedures can be done within the  $\pm$ 7 days window period. If REPLAGAL is discontinued, regardless of the reason, the evaluations listed for Week 52 will be performed as completely as possible. Subject may visit the clinical site at schedules other than the scheduled visits for assessments as clinically warranted; these will be recorded as unscheduled visit. Unscheduled visit(s) will be recorded in the eCRF.

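### SAP 6.6.4 counts expected infusions to study exit rather than to the end of treatment, so an early stopper who attends safety follow-up can be charged one infusion too many

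*SAP*

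**What the plan says.** SAP 6.6.4 gives compliance as "Number of Complete Infusions Received) / (Expected Number of Infusions)] ×100", and says that it "will be calculated as follows for up to 52 weeks". The expected number is "the number of infusions that the subject would have received up to the date of the subject's withdrawal or completion from the study". The measure is described as "reflecting the subject's willingness to accept the intravenous infusion at each infusion visit". A partial "infusion is defined when the infusion has been withdrawn / stopped and not completed", and partial infusions are left out of the numerator. The SAP also reports the number and percentage of subjects who received at least 80% "of scheduled infusions (not including partial infusions) will be reported", and tabulates missed infusions as 0, 1, 2 to 5, and more than 5.

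On timing, Protocol 8.1.3.1 is headed "REPLAGAL Infusion EOW (±4 days) from Week 0 Through Week 52". Protocol 7.1 covers stopping product and 7.3 covers withdrawal from the study, as separate events. Under 7.1, the date on which product was discontinued must be recorded in the source documents. The same section adds: "Whenever possible, all discontinued subjects should also undergo the protocol-specified safety follow-up 14 days (+7 days) after the last dose/infusion". Protocol 8.1.4 labels that contact the end of study and, for early stoppers, times it from the last infusion.

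**The concern.** The denominator runs past the point at which treatment ended. A subject who stops product but attends the requested follow-up is still in the study when the next infusion would have fallen due, so the SAP definition can count that infusion as expected although treatment was already over. A subject who stops at the same point and leaves within 13 days is not charged. The subject who co-operates more with the protocol therefore gets the lower score.

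The results at stake are the compliance percentage, the share of subjects at 80% or above, and possibly the missed-infusion categories. In a study of 20, each reclassified subject moves a reported share by 1/20 = 5 percentage points.

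**Working it through.** The documents give no worked compliance value and no expected infusion count, so there is no planned figure to reproduce. The check applies the SAP formula to the protocol schedule.

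**Inputs**
- Infusions every 14 days from Week 0 through Week 52 (Protocol 8.1.3.1): nominal days 0, 14, ..., 364, which is 364/14 + 1 = 27. The documents do not state 27; it is derived.
- Cut-off at withdrawal or completion from the study, capped at 52 weeks (SAP 6.6.4).
- End of study for an early stopper: 14 to 21 days after the last infusion (Protocol 8.1.4).
- Drop-out 10% to 20% (Protocol 6.5); 20 subjects (SAP 4.0).

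**Formula.** Let k be the infusions received, all complete, and g the days from the last infusion to the exit date. On the nominal schedule, expected = k + floor(g/14), never more than 27. An infusion due on the cut-off day counts as expected.

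**Exit before the next due date (g = 7 or 13).** floor(g/14) = 0, so compliance = k/k = 100%.

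**Exit at follow-up (g = 14 to 21).** floor(g/14) = 1, so compliance = k/(k+1):

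| Infusions received, all complete (k) | Expected | Compliance | At least 80%? |
|---|---|---|---|
| 1 | 2 | 50.0% | no |
| 2 | 3 | 66.7% | no |
| 3 | 4 | 75.0% | no |
| 4 | 5 | 80.0% | yes |
| 5 | 6 | 83.3% | yes |
| 13 | 14 | 92.9% | yes |
| 26 | 27 | 96.3% | yes |

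The condition k/(k+1) ≥ 0.80 is met exactly when k ≥ 4. Only a stop after one, two or three infusions crosses the threshold.

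**Completers.** Follow-up falls at about Week 54, but the cap holds expected at 27, so 27/27 = 100%.

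**Subjects exposed.** 20 × 0.10 = 2 and 20 × 0.20 = 4. This is a ceiling: it assumes that every drop-out has an exit date on or after the next due infusion.

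**After the change.** With the cut-off at product discontinuation and no infusion due between the last dose and that date, compliance = k/k = 100% for every k.

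**The case against.** The strongest reply is that the extra charge depends on a date the SAP leaves open. It does not say which recorded date is the withdrawal date for a subject who stops product. Protocol 7.3 describes withdrawal as being off treatment with no further visits, which could put it at or near the last dose. Follow-up after discontinuation is asked for only where possible, and the reasons for discontinuation in Protocol 7.2 include death and loss to follow-up. If the date falls before the next infusion is due, nothing is charged. This stands, and it limits the point to a conditional one. It does not remove it, because Protocol 8.1.4 dates end of study at the follow-up contact for the subjects who do attend.

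Second, Protocol 6.2.4 allows ±4 days around each infusion and speaks of a missed infusion when 21 days have passed since the previous dose. Follow-up falls on days 14 to 21, so on that wording nothing has yet been missed. This also stands for the missed-infusion table: SAP 6.6.4 does not define missed, so a move from category 0 to 1 is possible but not certain.

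Third, a subject who declines a due infusion and then leaves has shown the unwillingness that the measure is meant to capture. That is fair, and the replacement definition must keep such a refusal visible.

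Fourth, the effect is small. If stops were spread evenly over the 26 possible early stopping points (an assumption), 3/26 of 2 to 4 drop-outs is about 0.2 to 0.5 subjects falling below 80%. The SAP also plans a by-subject listing of all exposure data, so individual cases can be seen.

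A reader might go further and infer that scoring a stopped infusion as zero is a second error. The documents do not support that. The SAP excludes partial infusions explicitly, in both the numerator and the 80% category, and an infusion interrupted and then restarted under Protocol Appendix 3.1 can still be completed. Counting started infusions instead would be a more lenient choice with its own drawback, since it credits incomplete doses. The partial rule also plays no part in creating the extra expected infusion.

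**Conclusion.** The point holds in conditional form. SAP 6.6.4 ties the denominator to leaving the study, while the protocol keeps early stoppers in the study for 14 to 21 days after the last infusion. If the exit date is the follow-up contact, a subject who took every infusion scores k/(k+1), which is below 80% for k = 1 to 3 only. One missed infusion may also be counted.

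It would be too strong to infer that every early stopper is scored as missing a dose, or that early stoppers in general fall below 80%. The first depends on the recorded date and the second on stopping within the first three infusions.

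The conclusion assumes a nominal 14-day schedule and that an infusion due on the cut-off day counts as expected. Within the ±4-day window, a last dose given four days late brings the next nominal date to day 10 after it, and one given four days early moves it to day 18, so some follow-up contacts would fall before the next due date. At most 2 to 4 of 20 subjects are exposed. The effect is confined to descriptive compliance and missed-infusion summaries: SAP 3.1 tests no hypothesis, and SAP 5.4 defines the per-protocol set by major deviations, with no stated link to 80% compliance. This is a minor correction worth making.

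**What to change.** In SAP 6.6.4, define expected infusions as those scheduled from Day 1 up to the recorded date of investigational product discontinuation, or Week 52 for subjects who do not stop early. An infusion that fell due and was refused before that date still counts as missed. State how an infusion due on the discontinuation date itself is handled.

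The cost is one or two sentences and a change to one derivation. Protocol 7.1 already requires the discontinuation date in the source documents, so no new assessment is needed; the sponsor should confirm that the date is also in the analysis database.

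Keep the exclusion of partial infusions from the numerator. Saying whether a partial infusion counts as missed, and showing partial infusions on their own line, would be a useful but optional clarification.
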